## 21.0 Statistical Considerations

**21.1** General Description: This is a single-arm, Phase II trial to characterize the clinical outcome of standard of care, cetuximab concurrent with radiation, in a special population (head and neck cancer patients who cannot tolerate concurrent chemoradiotherapy due to advanced age, poor performance status or concurrent illness), and to determine if biomarker response to a loading dose of cetuximab is predictive of that outcome.

**21.2** Number of patients: Fifty evaluable patients will be accrued to the trial, which is expected to take 36 months. A patient will be evaluable for the primary objectives if he or she undergoes Research Biopsy #1 and #2 and either completes the full course of cetuximab+RT or has cetuximab+RT stopped for toxicity. Unevaluable patients will be replaced.

**21.3** Analysis plan

**21.3.1 Primary Objective 1:** Determine changes in tumor EGFR, pEGFR, downstream signaling and novel phosphoproteins following a loading dose of cetuximab in patients who are poor candidates for chemoradiation (age  $\geq 70$  years or with significant co-morbidities) and are therefore treated with cetuximab+radiation. These markers will be assessed in tumor biopsies harvested before and after the loading dose of cetuximab. The initial analysis will use descriptive and graphical statistics to determine if any of the markers require transformation prior to analysis. Markers may be assessed on a continuous, ordinal or

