dichotomous scale; markers measured on a continuous scale will be analyzed via general linear models (possibly after transformation), while ordinal and dichotomous markers will be analyzed via cumulative logit and logistic regression analyses, respectively. The primary questions to be answered in this objective are: is the marker modulated by the loading dose of cetuximab; are there baseline clinical or demographic variables that are related to significant variation in biomarker response to the loading dose of cetuximab? For continuous variables, the null hypothesis that the mean value of the change (absolute or percent of baseline) equals zero will be tested by means of a single sample t-test. The second question will be answered by means of analysis of variance on baseline clinical and demographic variables. For dichotomous markers, patients will be stratified into elevated versus not elevated at baseline, and Wald tests on logistic regression parameter estimates will be used to test the null hypothesis that the proportion of patients changing state from baseline is different from 0.5, and to determine if any subset of patients defined by clinical or demographic factors have proportions significantly different from 0.5. Ordinal markers will be handled in a similar fashion.

[figure not shown]
21.3.2 **Primary Objective 2** Characterize clinical outcomes, including local recurrence, progression-free survival and overall survival in these patients, and correlate these clinical outcomes with the changes in tumor EGFR, pEGFR, downstream signaling, and novel phosphoproteins. Logistic regression and proportional hazards (Cox) regression will be used to relate clinical out (local recurrence, progression-free survival or overall survival) to changes in markers across the loading dose. All of the markers will be analyzed, but markers that are modulated by the loading dose (identified in Primary Objective 1) will be of particular interest.

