### **Immunohistochemistry and Scoring of TMA:**

Antigen is retrieved from formalin-fixed tumor sections, in citrate buffer using a pressure cooker. Standard procedures are used for immunofluorescence. One high-density TMA will be constructed using a manual tissue arrayer (Beecher Instruments, [name], USA) at the core facility at the University of Michigan using standard methods. Tissue cores from the regions of interest (tumor

tissues, before and after treatment) will be targeted for transfer to the recipient array block. At least three 0.6 mm diameter replicate tissue cores will be sampled from each subregion of the selected sample. The final TMA will consist of approximately 200 cores. After construction, 4  $\mu$ m sections will be cut, and hematoxylin and eosin staining will be performed on the initial slide to verify the histology. Serial 4  $\mu$ m sections will be further cut and transferred to positively charged slides, these sections will be subjected to standard immunohistochemical staining procedures. Use of this established core enables the investigators to have access to over 200 commercially available antibodies that have been tested and validated for immunohistological use. Any antibodies not previously validated will be tested on slides made from "test arrays". These are tissue microarrays prepared from multiple tissue sources (e.g. normal mucosa, skin, brain, lymph nodes, gut, lung, spleen, liver, kidney etc., plus corresponding neoplastic tissues) created by the UM Cancer Center Tissue Procurement Core and available to the investigators. The stained test slides will be reviewed by certified pathologist for the expected pattern and appropriate intensity. The information about expected and appropriate staining for each antibody will be discussed with the other investigators to confirm the scoring criteria. The TMAs will be then stained by the staff at the Tissue Core. Each tissue core will be scored by a board certified oral and maxillofacial pathologist who is blinded as to the identity of the cores. Each tissue core will be scored for intensity of SCC cells staining: 1, undetectable; 2, weak; 3, moderate; 4, strong. An example of TMA cores is shown in Figure 2. Data analysis will be performed by [name]. Multiple TMA core measurements from the same subject will be averaged. This average score in its continuous scale will be used in all analyses.

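### Section 21.3.1 relates continuous-marker change to clinical factors without the baseline marker value, so a factor associated with starting level can look like a determinant of response to cetuximab

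*Combined protocol and SAP*

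**What the plan says.** Section 21.2 sets the size ("Fifty evaluable patients will be accrued to the trial, which is expected to take 36 months") and makes Research Biopsies #1 and #2 a condition of evaluability. Section 21.3.1 confirms the paired design: "These markers will be assessed in tumor biopsies harvested before and after the loading dose of cetuximab".

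For continuous markers, 21.3.1 gives three statements:
- Model family: "markers measured on a continuous scale will be analyzed via general linear models (possibly after transformation").
- First question, whether the marker is modulated: "the null hypothesis that the mean value of the change (absolute or percent of baseline) equals zero will be tested", by a one-sample t-test.
- Second question, whether baseline clinical or demographic variables relate to variation in that response: "The second question will be answered by means of analysis of variance on baseline clinical and demographic variables".

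The last sentence does not name its dependent variable. Following directly on the test of change, it is read here as change. No baseline marker covariate is listed.

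For dichotomous markers the same section does condition on the starting state: "patients will be stratified into elevated versus not elevated at baseline". Ordinal markers are to be handled similarly.

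Appendix B (Immunohistochemistry and Scoring of TMA) sets the scale: "Each tissue core will be scored for intensity of SCC cells staining: 1, undetectable; 2, weak; 3, moderate; 4, strong". Core scores are averaged within subject, and "This average score in its continuous scale will be used in all analyses". Tissue-array markers therefore fall into the continuous branch, the only one that leaves baseline out.

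**The concern.** The tissue-array score has a floor. A tumour scored 1 cannot fall, while a tumour scored 4 can fall by 3. If the loading dose lowers the marker, tumours that start higher have more to lose. A characteristic associated with starting level (tumour site or skin versus mucosal primary, for example) will then be associated with change even if the drug removes the same share of detectable signal from every tumour. The report could name a subgroup as responding differently when it only started elsewhere.

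For a characteristic unrelated to starting level there is no such bias. Leaving out a covariate that every evaluable patient already has then gives away precision in a 50-patient trial. These are separate consequences for separate kinds of factor.

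**Working it through.** **The plan's own figure.** The documents state no power for this question. The only stated power, in 21.4, concerns Objective 2: at least 80% at 1.1 standard units. A simulation with the inputs given there (50 patients, 36 months' accrual, median 22 months, analysis six months after the last patient) gives 84.7% at 1.1 and 78.1% at 1.0. The stated bound holds, but it does not bear on the second question of Objective 1.

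**Inputs.** From the documents: 50 evaluable patients, the 1-4 score, change as absolute or percent. Assumed: two groups of 25, two-sided alpha 0.05 (21.3.1 gives no alpha), pre-post correlation rho, and the simulation settings below.

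**1. Why the floor matters.** Let every tumour lose half its signal above 1, and compare starting scores of 2.4 and 2.9.
- Absolute change: -0.5 x 1.4 = -0.70 and -0.5 x 1.9 = -0.95. The difference is 0.25.
- Percent change: -0.70/2.4 = -29.2% and -0.95/2.9 = -32.8%.
- Log ratio: ln(1.70/2.4) = -0.345 and ln(1.95/2.9) = -0.397.

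The drug effect is identical by construction, yet the groups differ on all three change scales. Percent and log shrink the difference but do not remove it, because undetectable is 1 and not 0.

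**2. Size of the artefact.** True baseline means are 2.4 v 2.9, SD 0.6, limited to 1-4. Post = 1 + 0.5 x (baseline - 1) + N(0, 0.3), with measurement error added to both readings. Share of trials declaring a group effect:

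| Analysis | Error SD 0 | 0.2 | 0.3 |
|---|---|---|---|
| Absolute change | 54% | 40% | 30% |
| Post value, baseline-adjusted | 5-7% across the three | | |

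Percent or log change rejects in 12-21% over the same settings. With no baseline gap, all analyses reject in about 5%.

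**3. Precision, for a factor unrelated to baseline.** In units of the marker variance, the residual variance is 2(1 - rho) for change (48 df) and 1 - rho^2 with the covariate (47 df), a ratio of (1 + rho)/2. The standard error of the group difference is sqrt(variance x 4/50). At rho 0.5 the variances are 1.00 and 0.75, and power for a 0.7 SD difference is 67.9% v 79.9%, a gain of 12.0 points. Other settings (points gained):

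| Power using change | rho 0.3 | 0.5 | 0.7 | 0.8 |
|---|---|---|---|---|
| 60% | 18 | 12 | 7 | 4.5 |
| 80% | 13.5 | 10 | 6 | 4 |
| 90% | 8 | 6 | 4 | 3 |

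**4. Precision, for a factor linked to baseline.** If the factor correlates r with baseline, the ratio becomes (1 + rho)/2/(1 - r^2). At rho 0.5 it is 0.75, 0.82, 1.00 and 1.47 for r = 0, 0.3, 0.5 and 0.7. The gain disappears and then reverses.

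**5. Where adjustment misleads.** Take a marker that the drug does not move, a 0.5 gap between groups, and error SD 0.3-0.5. Change holds 5%; the adjusted model rejects in about 10-17%. More generally, with a stable 0.5 SD gap and equal true change, the adjusted model rejects in 23%, 15% and 9% at rho 0.3, 0.5 and 0.8, and change stays near 5%.

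**The case against.** The strongest objection is that the simulation in step 2 puts both groups on one common line from baseline to post value, which is the model under which baseline adjustment is correct. Patient characteristics are not randomised. If groups differ stably and truly change by the same amount, change scores are valid and adjustment creates the false positive (Lord's paradox; step 5). This stands. A reader might infer that any factor linked to baseline will pass as a determinant of response, or that adjustment alone is the safe analysis. The documents support neither, since they do not say which model holds for any marker.

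Second, the plan allows transformation and percent change. For a ratio-scale marker such as immunoblot density this is a real answer: with equal fractional loss, absolute change rejected in 59% of simulated trials, but percent change and log ratio in 5% each. It is not an answer for the tissue-array score (steps 1 and 2).

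Third, general linear models could include a baseline covariate. They could, but the sentence on the second question names only clinical and demographic variables, so nothing commits the analyst to it.

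Fourth, the question drives neither the sample size nor any stopping decision. That limits the stakes, though it is one of the primary questions listed under Primary Objective 1.

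**Conclusion.** The point holds in limited form. The continuous branch of 21.3.1 omits a covariate that every evaluable patient has and that the dichotomous branch uses in stratified form. On the floor-bounded tissue-array score, when the drug lowers the marker, a factor associated with starting level can be reported as a determinant of response: about 30-54% of trials with absolute change and 12-21% with percent or log change, against 5-7% with adjustment. These rates rest on the assumed half loss of signal, 0.5 gap and error SD of 0-0.3; they illustrate the mechanism and do not predict this trial.

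For factors unrelated to baseline the cost is roughly 3-18 points of power over rho 0.3-0.8 and starting power 50-90%. A reader might take the 12 points at rho 0.5 as the cost of the plan. The documents give no rho, no factor effect and no target power for this question, so that is one scenario within the range. Nor do the precision loss and the bias apply to the same factor.

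Neither analysis is safe alone, so both should be prespecified and read together.

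**What to change.** Replace the sentence on the second question in 21.3.1 with:

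> For continuous markers, the second question will be answered by a general linear model of the post-loading-dose value (on the transformed scale chosen for the first question) on the clinical or demographic variable with the baseline marker value as covariate; the unadjusted analysis of change on the same scale will be reported alongside, and a factor will be described as related to biomarker response only if the two analyses agree in direction and substance.

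The first question, the test of mean change, is unaffected. The cost is one sentence, one degree of freedom per model and no new data. The agreement rule is deliberately cautious: some real associations will be left as unresolved when the two analyses differ. It is needed because adjustment can produce a spurious effect when groups differ stably at baseline, truly change equally and the assay is noisy.

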**21.4 Justification of Design:** While radiation with concurrent cetuximab has become the standard of therapy in patients with locally advanced squamous cell head and neck carcinoma, the clinical outcome of the therapy have not been systematically studied. In addition, therapy with cetuximab is expensive, and, while less toxic than platinum-based therapies, is not without toxicity, and a screen for patients from whom cetuximab would be of benefit would be desirable. Therefore, all patients on this protocol are treated the same, and the primary objectives are focused on comparing patients who do respond to patients who do not. Because this is the standard of care, and these patients have no other treatment options, there is no provision for halting the trial due to low efficacy or excess toxicity (although therapy can, of course, be stopped in individual patients if clinically warranted). The sample size is justified in terms of Primary Objective 2, specifically relating change in a continuous marker to progression-free survival. Monte Carlo simulation was used to simulate the analysis of a single biomarker related to progression-free survival. It was assumed that 50 patients were accrued over 36 months, that the median survival was 22 months, the proportional hazards regression was performed six months after the last patients was treated, and that the biomarker was normally distributed. The power of the null hypothesis of no marker effect (tested at  $\alpha=0.05$ ) was assessed as the effect size of the marker (here, represented as the difference between the mean of the marker for patients with PFS less than the median versus the mean of the marker for patients with PFS greater than the median, divided by the standard deviation) was increased from 0 to 1.5 standard units. The result is shown in Figure 20.1, where it is seen that the power to reject the null hypothesis of no effect is at least 80% if the effect size is 1.1 standard units or greater, which would be considered a moderately large effect.

*Figure 20.1* Power of proportional hazards regression for a marker that discriminates between patients with greater than versus less than median progression-free survival.

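### The Wald test set for dichotomous markers in 21.3.1 returns p near 1 when every tumour in a stratum changes state, so a uniform switch would be reported as not significant

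*Combined protocol and SAP*

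**What the plan says.** Section 21.3.1 (Primary Objective 1) asks first whether each marker is modulated by the loading dose, and second whether baseline clinical or demographic variables relate to that response. Continuous markers go to a one-sample t-test and linear models. For the rest, "For dichotomous markers, patients will be stratified into elevated versus not elevated at baseline". The method that follows is this: "Wald tests on logistic regression parameter estimates will be used to test the null hypothesis that the proportion of patients changing state from baseline". As worded, that null is a proportion other than 0.5, which is really the alternative; I take the null to be a proportion of 0.5. The same tests have a second purpose: "to determine if any subset of patients defined by clinical or demographic factors have proportions significantly different from 0.5". The section adds: "Ordinal markers will be handled in a similar fashion".

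Section 21.2 sets the size: "Fifty evaluable patients will be accrued to the trial, which is expected to take 36 months". No stratum sizes, expected switch rates or significance level are given for this objective. No exact, score, likelihood-ratio or penalised alternative is named for a stratum in which all or no patients change. The plan does use an exact binomial method elsewhere, for the toxicity proportion in 21.3.3.

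**The concern.** A Wald statistic divides an estimate by its standard error. On the logit scale, as the observed proportion approaches 0 or 1 the standard error grows faster than the estimate, and at 0 or 1 the estimate has no finite value. The statistic then collapses to zero. The test therefore fails on the result that departs most from 0.5.

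At stake is the answer to the first question of a primary objective. A dichotomous marker that switched in every tumour of its stratum would be labelled not significantly modulated, while one that switched in all tumours but one could be labelled modulated. Section 21.3.2 gives particular interest to markers identified as modulated under Objective 1, so the label carries forward. Fifty patients divided by baseline state and then by clinical subset leave small cells, where all-or-none results are most likely.

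**Working it through.** **Inputs.** N = 50 (21.2). Null proportion 0.5 (21.3.1). Two-sided alpha of 0.05 is assumed; 21.4 states 0.05 only for the Objective 2 power simulation. Stratum sizes (5 to 50) and true switch rates (80% to 95%) are assumed ranges, because the plan gives neither.

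**The plan's own power figure.** The only one is in 21.4, for a continuous marker and progression-free survival: "It was assumed that 50 patients were accrued over 36 months, that the median survival was 22 months", with power "at least 80% if the effect size is 1.1 standard units or greater". A simulation on those assumptions (exponential times, uniform accrual, 4,000 runs per point) gives 78% at 1.0 SD and 85% at 1.1 SD, which agrees. It does not bear on the test examined here.

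**Step 1: Wald test.** For x of n changing, b = ln(x/(n−x)), SE = √(1/x + 1/(n−x)) and z = b/SE.
- 9/10: 2.197/1.054 = 2.08, p = 0.037.
- 24/25: 3.178/1.021 = 3.11, p = 0.0018.
- 10/10: no finite b. A standard GLM fit stops at b = 22.57, SE = 15,241, p = 0.999.
- 25/25: p = 0.999 again. The none-change case is the same with the sign reversed.

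**Step 2: alternatives at x = n.** The exact two-sided p is 2 × 0.5ⁿ:
- n = 5: 2/32 = 0.0625
- n = 6: 2/64 = 0.031
- n = 8: 2/256 = 0.0078
- n = 10: 2/1,024 = 0.002
- n = 25: 2/33,554,432 = 6e-8

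The likelihood-ratio statistic, 2n·ln 2, also stays finite: 13.9 at n = 10 (p = 2.0e-4) and 34.7 at n = 25 (p = 3.9e-9).

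**Step 3: small cells.** The smallest Wald p occurs at x = n−1, where z = ln(n−1)/√(1/(n−1) + 1):
- n = 6: 1.609/1.095 = 1.47, p = 0.14
- n = 7: 1.792/1.080 = 1.66, p = 0.097
- n = 8: 1.946/1.069 = 1.82, p = 0.069

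No outcome rejects at these sizes, whereas the exact test rejects at 0/n and n/n. At n = 5 neither test can reject.

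**Step 4: where the decisions differ.** Over every outcome for n = 5 to 50, the exact test rejects and the Wald test does not only at 0/n and n/n, and only from n = 6. At some sizes an outcome near the critical value goes the other way. For example, 11/14 gives Wald z = 1.299/0.651 = 1.99, p = 0.046, against exact 2 × 470/16,384 = 0.057. That is ordinary conservatism of a discrete test. At n = 10 and n = 25 the two tests agree at every outcome short of all or none.

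**Step 5: power.** At n = 10 and n = 25 the loss is the chance that all change, (true rate)ⁿ; the chance that none change is negligible.

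| n | True rate | Chance all change | Wald power | Exact power |
|---|---|---|---|---|
| 10 | 95% | 60% | 32% | 91% |
| 25 | 80% | 0.4% | 89% | 89% |
| 25 | 90% | 7% | 93% | 99.8% |
| 25 | 95% | 28% | 72% | 100% |

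**Step 6: between-subset comparisons.** The second question of 21.3.1 implies these without spelling them out. If used, they fail in the same way: 8/8 against 20/42 gives Wald p = 0.999 and Fisher p = 0.006.

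**The case against.** The strongest reply is that the reach is narrow. Appendix B averages tissue-microarray core scores and keeps them continuous in all analyses, and it quantifies immunoblot bands by densitometry. The naturally binary assays (HPV, p53, EGFRvIII) are not named in the Objective 1 statement. This stands as a limit, but it does not remove the problem. Section 21.3.1 provides expressly for dichotomous and ordinal markers, section 1.3 lists EGFRvIII status among the candidates whose change may predict response, and Appendix B grades TUNEL staining on an ordered scale.

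A reader might infer that all-or-none switching is the expected result with an EGFR antibody. The documents do not say so. Sections 1.1 and 1.3 anticipate tumours that do not show the changes, and 21.4 frames the objectives as comparing responders with non-responders. The high switch rates above are therefore scenarios, not forecasts.

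A reader might also infer that affected markers drop out of Objective 2. They do not: 21.3.2 analyses all markers, and modulation only adds interest. A marker that changes in every tumour of a stratum could not discriminate outcome within it in any case.

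Finally, software usually warns of separation, and an analyst would see 25/25 in a table. That makes a silent error less likely. The plan still gives no rule for what to do next, so the primary-objective test would be chosen after seeing the data.

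**Conclusion.** The concern holds for markers scored dichotomously, and the wording should be fixed before analysis. As written, the test returns p near 1 for a stratum or subset in which every tumour changes state, and it cannot reject at all with 6 to 8 patients. Rejections are lost only at 0/n or n/n, and only from n = 6. The size runs from nothing material (n = 25, true rate 80%) to a fall from 91% to 32% (n = 10, true rate 95%). These figures rest on an assumed two-sided 0.05 and on assumed stratum sizes and switch rates.

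Two stronger readings are not supported. One is that Primary Objective 1 fails as a whole: the averaged tissue-microarray scores and other continuous markers are untouched. The other is that a non-significant result when no tumour changes hides a biomarker response: no change is a departure from 0.5, but it is not modulation.

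**What to change.** In 21.3.1, replace the Wald tests for dichotomous markers with exact binomial tests against 0.5 and Clopper-Pearson intervals, within each baseline stratum and subset. For any between-subset comparison, use Fisher's exact test or a likelihood-ratio test from Firth-penalised logistic regression. In the cumulative-logit models for ordinal markers, use likelihood-ratio rather than Wald tests. State the significance level and word the null as a proportion equal to 0.5.

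The exact test will also reject when nothing changes: 0 of 25 elevated tumours switching off gives p = 6e-8. The text should therefore say that modulation is claimed only when the estimate and its interval lie on the side of change.

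The cost is a few sentences and standard software, with no new data or patients. The plan already uses an exact binomial interval for toxicity, so the method is not new to it.

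### For dichotomous markers, Primary Objective 1 tests modulation against 50% of patients changing state, which is not a no-effect value

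*Combined protocol and SAP*

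**What the plan says.** Section 21.3.1 (Primary Objective 1) poses two questions. The first is "is the marker modulated by the loading dose of cetuximab". The second is "are there baseline clinical or demographic variables that are related to significant variation in biomarker response".

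The section allows several measurement scales: "Markers may be assessed on a continuous, ordinal or" dichotomous. For continuous markers it tests "the null hypothesis that the mean value of the change (absolute or percent of baseline) equals zero". For dichotomous markers it stratifies patients by whether the marker is elevated at baseline, then applies Wald tests on logistic regression estimates to "the null hypothesis that the proportion of patients changing state from baseline is different from 0.5". Subsets defined by clinical or demographic factors are examined to see whether they "have proportions significantly different from 0.5". For the remaining scale it says only: "Ordinal markers will be handled in a similar fashion".

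The result is carried forward in Section 21.3.2, where "markers that are modulated by the loading dose (identified in Primary Objective 1) will be of particular interest", although every marker is analysed there. No reason is given for 0.5, and no alpha, stratum size or power is given for this test.

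**The concern.** The continuous and dichotomous branches answer the same question with different kinds of null. Zero mean change is a no-effect value. A 50% change rate in a baseline stratum is not.

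The value 0.5 belongs to a different quantity. Among discordant pairs, no effect means that off-switches and on-switches are equally likely. Once patients are stratified by baseline state, however, every change within a stratum goes the same way, and the patients who do not change are in the denominator. There, one half is the no-effect value only by coincidence.

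Two further defects follow. Testing each subset against 0.5 does not show whether response varies between patients: two subsets with identical switching proportions but different sizes can differ in significance. And the Wald test gives no usable result when none or all of a stratum change, although those are the clearest outcomes.

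The main harm is not a false claim of modulation. A reader who looks at direction would not call significantly fewer than half changing modulation. The harm is that real switch-off in half of tumours or fewer cannot be shown by this test.

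**Working it through.** **Inputs.** From the documents: 50 evaluable patients (Section 21.2); the test and its reference value (Section 21.3.1); 42% of tumours expressing EGFRvIII in a cited series (Section 1.3), hence 0.42 × 50 = 21. Assumed, because not given for this test: two-sided alpha 0.05, stratum sizes of 10 to 50, and misclassification rates. The plan states no operating characteristic for this test, so there is no figure to reproduce.

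**1. Rejection region.** With x of n patients changing, z = ln[x/(n−x)] / √[1/x + 1/(n−x)], significant if |z| > 1.96. For n = 25:
- x = 17: ln(17/8) = 0.754, SE = √(1/17 + 1/8) = 0.429, z = 1.76, not significant.
- x = 18: ln(18/7) = 0.944, SE = √(1/18 + 1/7) = 0.445, z = 2.12, significant.

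So 18/25 (72%) must switch to show a proportion above one half. The regions are 1 or 9 (n = 10); 1–5 or 16–20 (n = 21); 1–7 or 18–24 (n = 25); 1–17 or 33–49 (n = 50). When x = 0 or n, the logit is infinite. A fitted model gives p of about 1.0 at 0/25 and 25/25, but 0.002 at 1/25. These extreme outcomes are counted below as not significant.

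**2. Probability of significance.** Exact binomial sums over those regions:

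| True proportion switching | n = 21 | n = 25 | Side of 0.5 |
|---|---|---|---|
| 10% | 88% | 93% | all below |
| 30% | 36% | 51% | all below |
| 50% | 2.7% | 4.3% | split equally |
| 80% | 76% | 89% | all above |
| 90% | 88% | 93% | all above |

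At 50% switching, strata of 10, 25 and 50 give 2.0%, 4.3% and 3.3%. At 60% switching, significance above one half is 15% for n = 25 and 24% for n = 50.

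**3. What no effect implies.** Let q be the true proportion elevated, and let each biopsy be misclassified independently with probability e. With no drug effect:
- P(elevated, then not) = q(1−e)e + (1−q)e(1−e) = e(1−e)
- P(classed elevated at baseline) = q(1−e) + (1−q)e
- expected switch-off in the elevated stratum = e(1−e) / [q(1−e) + (1−q)e]

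With e = 0.10 the numerator is 0.09:

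| q | Denominator | Expected switch-off |
|---|---|---|
| 0.9 | 0.82 | 11% |
| 0.8 | 0.74 | 12% |
| 0.5 | 0.50 | 18% |
| 0.2 | 0.26 | 35% |
| 0.1 | 0.18 | 50% |

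No fixed benchmark suits all prevalences. By contrast, the joint off and on probabilities are both e(1−e) at any q, so the McNemar null holds throughout. Exact McNemar on 50 pairs rejects 0.8%, 2.1% and 2.8% of the time for e = 0.05, 0.10 and 0.20.

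**4. One example.** Suppose 10 of 25 elevated tumours switch off and 1 of 25 non-elevated tumours switches on. The planned test in the elevated stratum gives z = ln(10/15) / √(1/10 + 1/15) = −0.99, p = 0.32. Exact McNemar on 10 versus 1 gives p = 2 × (1 + 11)/2¹¹ = 0.012.

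**5. Power of exact McNemar.** By full enumeration, with switching proportions conditional on baseline state:

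| Elevated / not | Off / on | Power |
|---|---|---|
| 25 / 25 | 50% / 10% | 73% |
| 25 / 25 | 30% / 10% | 22% |
| 21 / 29 | 50% / 10% | 46% |
| 21 / 29 | 30% / 10% | 9% |
| 10 / 40 | 50% / 10% | 1% |
| 10 / 40 | 90% / 10% | 12.5% |

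In the last row the planned test in the elevated stratum of 10 has 38.7%.

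**The case against.** **No marker is tied to this test.** The plan only allows for dichotomous markers. Appendix B describes quantitative readouts: averaged tissue-microarray scores kept on a continuous scale, scanned blot bands and fluorescence intensities. The nearest candidate is EGFRvIII status. Appendix B splits both the pre- and post-treatment specimens and sends one part for DNA and RNA, but Section 13.4 mentions no RNA at the first biopsy, and Section 13.5 assigns a core to it only at the second. This limit on scope stands, and the stratum of 21 is illustrative. It does not make the rule correct where it applies.

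**Little depends on the result.** No sample size, stopping rule or marker exclusion uses it. That also stands: only the priority label in Section 21.3.2 is affected.

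**McNemar is weak when few tumours are elevated.** This is true. With 10 elevated and 40 not, 50% off gives 5 expected off-switches against 40 × 0.10 = 4 on-switches, so there is almost no net change to detect. McNemar also treats equal movement in both directions as no modulation. It therefore needs the stratum proportions beside it. It remains preferable to 0.5 because its null corresponds to no drug effect under equal measurement noise on both biopsies.

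**Ordinal markers may not be affected.** Fair: the plan does not say that 0.5 carries over to them.

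**Conclusion.** The concern holds. As written, the dichotomous analysis in Section 21.3.1 does not test whether the marker is modulated, and nothing elsewhere in the plan justifies 0.5. In a stratum of 25, a real switch-off in half of tumours is significant 4.3% of the time, and a real 30% switch-off is significant only on the side that reads as no modulation. Switching of 80% to 90% is found in 89% to 93% of trials.

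These figures rest on two-sided 0.05 and assumed stratum sizes; the range of no-effect values also rests on an assumed 10% misclassification. The reach is limited to markers analysed as dichotomous, possibly none, and the effect on Primary Objective 2 is one of emphasis. The point should be fixed because it concerns a primary objective and the correction is simple.

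**What to change.** In Section 21.3.1:

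- Delete the 0.5 benchmark and correct the wording of the null.
- For each dichotomous marker, test P(elevated, then not) = P(not, then elevated) with the exact McNemar test on before/after pairs.
- Report the proportion switching in each baseline stratum with exact confidence intervals. State that McNemar tests net change and has little power when few tumours are elevated at baseline, so the two are read together.
- For the second question, compare switching proportions between subsets within a baseline stratum: a covariate odds ratio of 1 in the logistic model already planned, or an exact test when cells are empty.
- State which markers, if any, are dichotomous and the cut used.
- Say what is meant for ordinal markers; a paired ordinal method such as the Wilcoxon signed-rank test would serve.

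The cost is a change to the analysis text of one section. No new data are needed and the sample size is unchanged.
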